#### **7.1.1.2 Washout Telephone Call (Group B)**

The washout period will be initiated after clinical laboratory test results and 12-lead ECG results have been received and reviewed by the investigator.

Eligible subjects will be contacted by a member of the site staff and provided with instructions on discontinuing any protocol-prohibited medications. During washout, a subject's current prohibited medications (if applicable) will be discontinued for a period of up to 32 days or 5 times the half-life of the medication, whichever is longer. Washout periods for prohibited medications are defined in [Table 3](#).

As part of the washout telephone call, site personnel will perform the following procedures:

- Schedule the baseline visit (Visit 2)
- Review the inclusion/exclusion criteria
- Ask about any concomitant medications that the subject is taking. If new concomitant medications that require washout are noted, instructions for appropriate washout will be provided
- Provide instructions on discontinuing any medication requiring washout
- Determine if any AEs have occurred since the screening visit (Visit 1)

If a medication washout is not necessary, the washout telephone call will include all the above procedures except providing instructions on discontinuing any current medications.

#### **7.1.1.3 Baseline Visit (Visit 2) Group A**

Visit 2 for subjects in Group A will be the same day as the final on-site visit for the antecedent study. During this visit, subjects will be screened for eligibility into study SHP465-308.

The investigator or designee must obtain written informed consent from the subject's parent/LAR before any SHP465-308 study-related procedures conducted during the baseline visit (Visit 2). There must also be documentation of assent (if required by IRB), indicating that the subject is aware of the investigational nature of the study and the required procedures and restrictions, before the performance of any SHP465-308 study-related procedures.

Inclusion/exclusion criteria must be reviewed during this visit to ensure subjects continue to meet all eligibility criteria.

[Table 1](#) (Group A) outlines all procedures to be conducted during Visit 2 and should serve as the primary point of reference regarding study procedures. Additional clarification on the procedures performed during the baseline visit (Visit 2) is provided as follows:

- Vitals will include oral or tympanic temperature, pulse, sitting blood pressure, and respiratory rate. Also, blood pressure and pulse will be collected 3 times (with at least 2 minutes in between each collection) using the age-appropriate cuff during the visit. The average of each set of 3 measurements will be used to determine continued participation in the study (Section 4.3.1).
- For eligible subjects, the investigator or assigned site staff designee will access the IWRS to enroll the subject and obtain an investigational product bottle number to dispense to the subject's parent/LAR. Sufficient investigational product will be dispensed to last until the next regularly scheduled visit. The parent/LAR responsible for dosing will be instructed to dispense 1 capsule each day to the subject. Dosing will begin the morning after the baseline visit (Visit 2).
- The C-SSRS "Since Last Visit" Version of the Pediatric/Cognitively Impaired Version should be completed.

#### 7.1.1.4 Baseline Visit (Visit 2) Group B

Once the screening central clinical laboratory tests and 12-lead ECG results have been obtained, in addition to repeat assessments (if required), and the subject has completed the required washout period (if applicable), the subject will return to the site for the baseline visit (Visit 2).

Inclusion/exclusion criteria must also be reviewed during this visit to ensure that the subject continues to meet all eligibility criteria.

Table 2 (Group B) outlines all procedures to be conducted during the baseline visit (Visit 2) and should serve as the primary point of reference regarding study procedures. Additional clarification on the procedures performed during the baseline visit (Visit 2) is provided as follows:

- For subjects with >32 days since the safety measurements at the screening visit (Visit 1) were collected, an abbreviated physical examination, vital signs, clinical laboratory tests, and 12-lead ECG in triplicate must be repeated, and the results reviewed by the investigator before the subject is enrolled.
- Blood pressure and pulse will be collected 3 times (with at least 2 minutes in between each collection) using the age-appropriate cuff during the visit. The average of each set of 3 measurements will be used to determine continued participation in the study (see Section 4.3.1).
- If >32 days since the screening visit (Visit 1), 3 ECGs will be taken, with approximately 3 minutes in between each one, to ensure that appropriate baseline intervals are established. The investigator will perform the initial interpretation of the ECG immediately after collection to ensure the safety of each subject to continue with the study. The ECG tracing will be sent to the central reader for analysis. Upon review of the report from the central reader, the investigator will re-evaluate the clinical significance of the ECG in light of other safety data for the subject. If abnormal and significant results are observed following assessment by the central reader, the investigator, in consultation with the appointed CRO medical monitor, will

confirm the subject's continued participation in this study.

- The C-SSRS "Since Last Visit" Version of the Pediatric/Cognitively Impaired Version should be completed.
- For eligible subjects, the investigator or assigned site staff designee will access the IWRS to enroll the subject and obtain an investigational product bottle number to dispense to the subject's parent/LAR. Sufficient investigational product will be dispensed to last until the next regularly scheduled visit. The parent/LAR responsible for dosing will be instructed to dispense 1 capsule each day to the subject. Dosing will begin the morning after the baseline visit (Visit 2).

### **7.1.2 Treatment Period (Group A and Group B)**

At each visit during the treatment period up to and including Visit 16, sufficient investigational product will be dispensed to last until the next regularly scheduled visit. The parent/LAR responsible for dosing will be instructed to dispense 1 capsule each day to the subject. At each visit, the subject's parent/LAR must return any empty or unused bottles to permit drug accountability and compliance to be assessed.

Throughout the treatment period, subjects may attend the clinic for unscheduled visits to address any medical needs that arise between scheduled visits.

[Table 1](#) (Group A) and [Table 2](#) (Group B) outline all procedures to be conducted during Visits 3 and 4 and should serve as the primary point of reference regarding study procedures. Further clarification for these visits is outlined as follows:

- At Visits 3 and 4, subjects must return any empty or unused bottles to permit drug accountability and compliance to be assessed.
- Subjects will be dispensed a 9-count bottle of investigational product to cover them until their next regularly scheduled visit. Subjects will be instructed to take 1 capsule each day. Dosing will begin the morning after each visit.
- Blood pressure and pulse will be collected 3 times (with at least 2 minutes in between each collection) using the age-appropriate cuff during the visit. The average of each set of 3 measurements will be used to determine continued participation in the study (see Section [4.3.1](#)).
- Scales should be completed by the same rater with input from the same parent/LAR whenever possible.
- The C-SSRS "Since Last Visit" Version of the Pediatric/Cognitively Impaired Version should be completed during Visits 3 and 4.

#### **7.1.2.1 Treatment Period (Visits 5 to 16/Early Termination)**

Subjects will continue daily morning treatment for an additional 12 months.

Throughout the treatment period, subjects may attend the clinic for unscheduled visits to address any medical needs that arise between scheduled visits.

[Table 1](#) (Group A) and [Table 2](#) (Group B) outline the procedures to be completed at each visit during the treatment period and should serve as the primary point of reference regarding study procedures. Additional clarification on the procedures to be performed during the treatment period Visits 5 to 16 is provided as follows:

- Scales are to be completed by the same rater with input from the same parent/LAR whenever possible
- At each visit during the treatment period, subjects must return any empty or unused bottles to permit drug accountability and compliance to be assessed
- Subjects will be dispensed a 9-count bottle of investigational product to cover them until their next regularly scheduled visit. Subjects will be instructed to take 1 capsule each day. Dosing will begin the morning after each visit.
- The C-SSRS “Since Last Visit” Version of the Pediatric/Cognitively Impaired Version should be completed during the treatment period.
- Blood pressure and pulse will be collected 3 times (with at least 2 minutes in between each collection) using the age-appropriate cuff during the visit. The average of each set of 3 measurements will be used to determine continued participation in the study (see Section [4.3.1](#)).

All subjects who complete the study or discontinue early will complete Visit 16/ET.

[Table 1](#) (Group A) and [Table 2](#) (Group B) outline all procedures to be conducted during Visit 16/ET and should serve as the primary point of reference regarding study procedures.

Further clarification on the procedures performed during Visit 16/ET is provided as follows:

- Unused investigational product and empty containers will be collected to calculate medication compliance.
- Blood pressure and pulse will be collected 3 times (with at least 2 minutes in between each collection) using the age-appropriate cuff during the visit. The average of each set of 3 measurements will be used to determine continued participation in the study (see Section [4.3.1](#)).

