**Table 1: Schedule of Assessments for Group A**

Period	Baseline	Treatment Period														1-Week Safety Follow-up Telephone Call
Visit a	2	3	4	5	6	7	8	9	10	11	12	13	14	15	16/ET b	
Assessment Week/Month	0	W1	W2	M1	M2	M3	M4	M5	M6	M7	M8	M9	M10	M11	M12	W53
Assessment Day	0	7	14	30	60	90	120	150	180	210	240	270	300	330	360	367
C-SSRS Since Last Visit version k	✓	✓	✓	✓	✓	✓	✓	✓	✓	✓	✓	✓	✓	✓	✓	
Suitability of subject to remain in study j	✓	✓	✓	✓	✓	✓	✓	✓	✓	✓	✓	✓	✓	✓		
Concomitant medications	✓	✓	✓	✓	✓	✓	✓	✓	✓	✓	✓	✓	✓	✓	✓	✓
Adverse Events	✓	✓	✓	✓	✓	✓	✓	✓	✓	✓	✓	✓	✓	✓	✓	✓
Access IWRS	✓	✓	✓	✓	✓	✓	✓	✓	✓	✓	✓	✓	✓	✓	✓	
Investigational product distributed	✓	✓	✓	✓	✓	✓	✓	✓	✓	✓	✓	✓	✓	✓		
Investigational product returned		✓	✓	✓	✓	✓	✓	✓	✓	✓	✓	✓	✓	✓	✓	
Investigational product compliance		✓	✓	✓	✓	✓	✓	✓	✓	✓	✓	✓	✓	✓	✓	

ADHD-RS-5=Attention-deficit/Hyperactivity Disorder Rating Scale 5, Child, Home Version; BMI=body mass index; CGI-I=Clinician’s Global Impression – Improvement; CGI-S=Clinician’s Global Impression – Severity of Illness; CSHQ=Children’s Sleep Habits Questionnaire; C-SSRS=Columbia-Suicide Severity Rating Scale; ECG=electrocardiogram; ET=early termination; IWRS=interactive web response system; M=month; MINI-KID=Mini International Neuropsychiatric Interview for Children and Adolescents; PSQ=Post Sleep Questionnaire; TEAEs=treatment-emergent adverse events; W=week.

a Visit windows are with respect to baseline (Visit 2): ±2 days for Visit 3-4 and ±5 days for Visit 5-16 during treatment period, and +2 days for the safety follow up telephone call.

b Subjects who terminate early will undergo the evaluations listed for Visit 16.

c Inclusion/exclusion criteria will be reviewed at baseline (Visit 2).

d Medical history will include all lifetime psychiatric and nonpsychiatric medications and procedures.

e Vital signs include oral or tympanic temperature, pulse, sitting blood pressure, and respiratory rate. The subject will have been seated for a minimum of 3 minutes before blood pressure, pulse, and respiratory rate measurements are taken. Measurement of blood pressure and pulse will be collected 3 times (with at least 2 minutes in between each collection) using the provided age-appropriate cuff. The average of each set of 3 measurements will be used to determine continued participation in the study.

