### 6.2 Administration of Investigational Product(s)

#### 6.2.1 Interactive Response Technology for Investigational Product Management

An interactive web response system (IWRS) will be employed in this study to manage the tracking and confirmation of shipments, supply, inventory, ordering, expiration, site assignments, and dosing of the investigational products.

The IWRS provider will provide a user manual and training to each site, with detailed instruction on the use of the IWRS.

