### **6.3.2 Packaging**

Investigational product is packaged in the following labeled containers:

SHP465 capsules are packaged in 9-count high-density polyethylene bottles with child-resistant closures.

Changes to sponsor-supplied packaging before dosing may not occur without full agreement in advance by the sponsor.

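### From Visit 4 on, the single 9-count bottle in Protocol 7.1.2 and 7.1.2.1 is too small for the interval that it is said to cover

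*Protocol*

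**What the plan says.** Protocol 7.1.2 opens with a general rule for every treatment visit: "At each visit during the treatment period up to and including Visit 16, sufficient investigational product will be dispensed", in an amount meant to reach the following visit. The baseline instructions state the same rule without a bottle count; for Group B, 7.1.1.4 reads "Sufficient investigational product will be dispensed to last until the next regularly scheduled visit".

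The visit-specific bullets then give a quantity. Section 7.1.2.1, for Visits 5 to 16, says "Subjects will be dispensed a 9-count bottle of investigational product to cover them until their next regularly scheduled visit", followed by "Subjects will be instructed to take 1 capsule each day. Dosing will begin the morning after each visit". Section 7.1.2 has the same wording for Visits 3 and 4. Section 6.3.2 gives only one pack size: "SHP465 capsules are packaged in 9-count high-density polyethylene bottles".

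Tables 1 and 2 place Visits 2, 3, 4 and 5 on Days 0, 7, 14 and 30, and later visits every 30 days to Visit 16 on Day 360. The windows are the same for both groups: "Visit windows are with respect to baseline (Visit 2): ±2 days for Visit 3-4 and ±5 days for Visit 5-16 during treatment period".

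**The concern.** The bullets are the only place where the protocol gives a quantity to dispense at Visits 3 to 16. The schedule tables are the primary reference for procedures, but they show only that product is dispensed, not how much. The quantity fits a weekly visit and is repeated unchanged for a 16-day interval and then for monthly ones.

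A site that followed the bullet literally would leave a child without study drug for most of each month, in a study of daily dosing with a controlled stimulant. A site that followed the opening rule of 7.1.2 would have to depart from the bullet. From Visit 4 the two instructions cannot both be met, except at the very shortest permitted gap between Visits 4 and 5.

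**Working it through.** **Inputs.** One capsule a day, starting the morning after each visit (7.1.2, 7.1.2.1). One bottle holds 9 capsules (6.3.2). Assessment days and windows are from Tables 1 and 2: ±2 days for Visits 3 and 4, ±5 days for Visits 5 to 16, all relative to baseline.

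**Formulas.** For visits on days d and e, doses fall on days d+1 to e, so capsules needed = e − d. Coverage by one bottle = min(1, 9/(e − d)). Bottles needed = (e − d)/9, rounded up.

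**The plan's own figure.** The sentence holds for Visit 3 to Visit 4 at nominal timing: 14 − 7 = 7 days, so 9 capsules leave 2 spare.

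**All intervals from Visit 3.**

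| Interval | Days, nominal (permitted) | Short at nominal | Coverage, nominal (permitted) | Bottles, nominal / longest |
|---|---|---|---|---|
| Visit 3–4 | 7 (3 to 11) | 0 | 100% (82% to 100%) | 1 / 2 |
| Visit 4–5 | 30 − 14 = 16 (9 to 23) | 7 | 9/16 = 56% (39% to 100%) | 2 / 3 |
| Each of 11 intervals, Visits 5–16 | 30 (20 to 40) | 21 | 9/30 = 30% (22.5% to 45%) | 4 / 5 |

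The permitted ranges come from moving both visits to opposite ends of their windows. For Visit 4–5 the shortest gap is 25 − 16 = 9 days and the longest is 35 − 12 = 23. For a monthly interval they are 30 − 10 = 20 and 30 + 10 = 40.

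At nominal timing one bottle is too little for 12 of the 13 intervals that start at Visits 3 to 15. For Visit 4–5 it is enough only at the 9-day extreme. For a monthly interval it is never enough.

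**Leftover capsules.** These do not close the gap. Families must bring back unused product and bottles at every visit (6.5, 7.1.2, 7.1.2.1). Even if the 2 spare capsules from Visit 3 were kept, the Visit 4–5 shortfall would fall only from 7 to 5, and no later interval leaves a surplus.

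**Nominal bottle counts against the windows.** An on-time Visit 4 followed by the latest Visit 5 is 35 − 14 = 21 days, and 2 bottles hold 18. At monthly visits 4 bottles hold 36, which covers an on-time visit followed by the latest permitted one (35 days) but not gaps of 37 to 40 days. One bottle at Visit 3 fails at 10 or 11 days.

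**The case against.** The strongest reply is that the bullet is loose wording about the pack, not a limit of one bottle. The correct rule opens the same section and appears in the baseline instructions. Section 6.2.1 says "An interactive web response system (IWRS) will be employed in this study to manage the tracking and confirmation of shipments, supply, inventory" and dosing, so sites would not work from the bullet alone. SAP 8.2 speaks of bottles, in the plural, dispensed at a single visit, and Protocol 6.5 provides for product returned in its sealed original container. Both fit dispensing several bottles.

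This stands as evidence of intent, and it is why the point is minor. It does not make the sentence right: the bullet is in the singular and says that this quantity covers the subject to the next visit. Section 6.2.1 states no quantity per visit, and no other text gives a bottle count that corrects it.

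A reader might infer that children were actually under-dosed, or that exposure and compliance results are compromised. SAP 8.2 treats 80–120% as compliant, and one bottle would cap a nominal monthly interval at 30%. The documents do not support that inference. They contain no dispensing data, and the surrounding text points to multi-bottle supply. The 30% cap only shows that the literal text cannot be what was intended.

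A reader may also notice that 7.1.2 has product dispensed at Visit 16, whereas the dispensing row in Table 1 has 14 ticks for 15 visits, consistent with Visits 2 to 15. The protocol makes the table the primary reference, so this is clerical and no edit is requested for it.

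**Conclusion.** The point holds as a wording and arithmetic error of minor severity. The stated quantity is wrong as 7.1.2 applies at Visit 4 and as 7.1.2.1 applies at Visits 5 to 15. One bottle covers 56% of the nominal Visit 4–5 interval and 30% of each nominal monthly interval, and it contradicts the sufficiency rule in 7.1.2. The sentence is adequate for Visit 3 at nominal timing.

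The result rests only on the one-capsule daily dose, the 9-capsule pack, the assessment days and the windows, all stated in the protocol. No sample size, endpoint, analysis set or SAP result depends on it. SAP section 1 records the sponsor's decision of 14 Dec 2018 to terminate the study, so the main value of a correction now is an accurate protocol and not carrying the sentence into another one.

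**What to change.** In both bullets, replace the single bottle with: enough 9-count bottles to last until the latest permitted date of the next scheduled visit. Check that the IWRS dispensing settings match.

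Bottle counts need not be printed. If they are, use those that cover the full windows (2 at Visit 3, 3 at Visit 4, 5 at each of Visits 5 to 15), or give the nominal counts (1, 2 and 4) with a note that they do not cover the windows.

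The cost is one edited sentence in each of two sections and a settings check, with no added visits, procedures or subjects. Protocol amendments need sponsor and ethics approval (10.3.2), but the amendment summary shows that earlier clarifications were first issued as administrative change memos, which may be enough here. Counts that cover the windows have a small downside: more unused controlled drug to return and reconcile at capsule level (6.4).

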### **7.1.3 Safety Follow-up Period (Group A and Group B)**

The follow-up period for this protocol is 7 days (+2 days) from the final dose of investigational product.

At the end of this period, there will be a telephone call initiated by the site staff to query for serious adverse events (SAEs), TEAEs, and concomitant treatments. All TEAEs and SAEs that are not resolved at the time of this contact will be followed to closure (see Section [8.1](#)).

#### **7.1.4 Additional Care of Subjects After the Study**

No aftercare is planned for this study. The investigator will discuss the available ADHD treatment options for subjects.

#### **7.2 Study Evaluations and Procedures**

The individual indicated in each scale description will perform all assessments listed as follows. Assessments are to be performed according to the schedule shown in [Table 1](#) (Group A) and [Table 2](#) (Group B). Care must be taken by the site personnel or the investigator to fully explain the scale before completion.

If the subject terminates treatment early, all assessments listed in [Table 1](#) (Group A) and [Table 2](#) (Group B) for Visit 16/ET and the safety follow-up call should be completed. Whenever possible, raters (including parent/LAR, and the investigator or site designee) observing the subject's behavior should be consistent from visit to visit throughout the study.

##### **7.2.1 Demographic and Other Baseline Characteristics**

Demographic characteristics such as age, sex, weight, height, and BMI will be collected throughout the study according to [Table 1](#) (Group A) and [Table 2](#) (Group B).

##### **7.2.1.1 Mini International Neuropsychiatric Interview for Children and Adolescents**

The MINI-KID is a structured clinical diagnostic interview designed to assess the presence of psychiatric disorders in children and adolescents in a way that is comprehensive and concise. It follows the structure and format of the adult version of the interview and is organized in diagnostic sections or modules. Using branching tree logic, the instrument asks 2 to 4 screening questions for each disorder. Additional symptom questions within each disorder section are asked only if the screen questions are positively endorsed. The MINI-KID is the structured psychiatric interview of choice for psychiatric evaluation and outcome tracking in clinical psychopharmacology trials and epidemiological studies. In a validation study ([Sheehan et al., 2010](#)), the MINI-KID generated reliable and valid psychiatric diagnoses for children and adolescents and does so in one-third of the time as the Kiddie Schedule for Affective Disorders and Schizophrenia Present and Lifetime Version. The standard MINI-KID Version 7.0.2 for DSM-5 assesses the 30 most common and clinically relevant disorders or disorder subtypes in pediatric mental health. With this version the child and parent are interviewed together. The MINI-KID should be completed by an individual who has experience in the evaluation of pediatric patients with ADHD and the scale, and may include physicians, or licensed psychologists/clinicians. All individuals performing this assessment must be preapproved by the sponsor or designee.

